Does the expression of Bmi-1 vary from oral epithelial dysplasia to different grades of squamous cell carcinoma at protein and molecular levels? Which one of them is more sensitive and specific for Bmi-1 assessment, the protein or molecular levels?

V. Methods:

Source of data:

Convenient consecutive sampling; it will include all archived blocks in the past 5 years (2012-2017).

Study design: Prospective cohort (In vitro validation study test)

Participants:

The archival paraffin embedded tissue samples which will be included in this diagnostic study are 30 samples of oral dysplasia and squamous cell carcinoma. We will apply a convenient consecutive sampling; it will include all archived blocks in the past 5 years (2012-2017) for this validation study. Excluded are samples of sarcomas or benign tumors or any carcinoma other than squamous cell carcinoma or any other techniques rather than immunohistochemistry or PCR. Samples that fulfilled the eligibility criteria will be included consecutively (consecutive sampling) until the target sample size will be reached. Data regarding Bmi-1 antibody expression in oral dysplasia and different grades of squamous cell carcinoma will be collected prospectively from both the reference and index tests independently.

Predictors:

Biopsy embedded in paraffin blocks was selected as reference standard method to assess the expression of Bmi-1 antibody at protein and RNA levels by immunohistochemistry and PCR respectively.

FIRST , PCR ANALYSIS

According to **Borbély et al 2007** tissue blocks will be prepared as follow:

- 1-** Tissue of 30 microns will be cut from paraffin blocks using scalpel and was put in eppendorf.
- 2-** 200 ml of tissue lysis buffer (ATL) + 0.6 ml of DNAs inhibitors + 10 ml proteinase K will be added to the sample.
- 3-** Sample will be incubated at 55 °C for 20 min.
- 4-** 250 micron of ethanol will be added and the sample will be left for 5min at room temperature.
- 5-** Sample will be collected by micropipette into spin column and will be centrifuged at 8000/ rpm for 1 min.
- 6-** 500 microlitre of wash buffer 1 will be added and the spin column will be centrifuged at 8000/ rpm for 1 min.
- 7-** 500 microlitre of wash buffer 2 will be added and the spin column will be centrifuged at 8000/ rpm for 1 min.
- 8-** 500 microlitre of elusion buffer will be added and the spin column will be centrifuged at 14,000/ rpm for 3 min.

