- 9-** 490 microlitre of distilled water will be added for each of DNA extracted sample.
- 10-** Spectrophotometer assessment will be done for concentration and purification of extracted nucleic acid (measurement of extracted nucleic acid 260/280 absorbance UV.

- 11- The sample will be divided into two portions in 200 ml eppendorfs.
- 12- The first portion will be added to SYBERGREEN for amplification and quantitation of Bmi-1 gene by real time PCR using APPLIED BIO SYSTEM (U S A).
- 13- The second portion will be added to SYBERGREEN for amplification and quantitation of Bmi-1 receptor gene by real time PCR using APPLIED BIO SYSTEM (U S A).

SECOND, IMMUNOHISTOCHEMISTRY

A-Reagents:

- 1- **Primary antibody** BMI-1 rabbit polyclonal antibody
- 2- **The universal immunostaining detection kit** (Dako Cytomation Envision+ Dual link system, Peroxidase (DAB+) Code K4065, Carpinteria, CA,USA).
- 3- **Buffer:** Phosphate buffer saline (PBS) of pH 7.4 (1.48 gm dibasic sodium phosphate anhydrous, 0.43 gm monobasic potassium phosphate anhydrous and 7.2 gm sodium chloride in one liter of distilled water).

B-Procedures:

- 1- **Deparaffinization:** The paraffin sections will be deparaffinized in three changes of xylene, and will be placed for 10 minutes in each change at room temperature.
The excess liquid will be drained and the slides will be transferred to alcohol, 15 minutes for each descending grades of concentrations (100%, 70% then 50%). Then the slides will be rinsed under tap water for 5 minutes.
Immersion of slides in PBS (2 changes), 5 minutes for each.
- 2- **Epitope retrieval:** Citrate Buffer Epitope Retrieval method will be used in this technique. Briefly, a steamer for water bath will be preheated with staining dish containing citrate buffer (ph 6.0) until temperature will be reached 95-100°C. Slides will be immersed in the staining dish and the lid will be loosely placed then will be incubated for 20 minutes and will turn off the steamer. The

staining dish will be placed at room temperature and will be allowed to cool for 20 minutes.

- 3- Primary antibody: sections will be incubated in rabbit anti-Bmi-1 individually for 1 hour at room temperature. Sections will be rinsed in 2 changes of washing buffer, 2 minutes each.

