- 4- Serum block: sections will be incubated with normal horse serum blocking solution for 30 minutes to block non-specific binding of immunoglobulin. The best results will be obtained with dilution 1:25. Slides will be rinsed in washing buffer for 2×2 min
- 5- Peroxidase blocking: sections will be incubated in peroxidase blocking solution for 10 minutes to block endogenous peroxidase activity.
- 6- Slides will be rinsed in washing buffer 3×2 min
- 7- Secondary antibody: sections will be incubated with biotinylated horse Anti-Mouse IgG diluted in secondary antibody dilution.
- 8- Slides will be rinsed in washing buffer 3×2 min.
- 9- Chromogen/substrate: sections will be incubated in DAB peroxidase substrate solution for 5-10 min and then will be rinsed with distilled water
- 10- Slides will be counter stained with Mayer's haematoxylin solution, then will be rinsed in running tap water for 5 minutes
- 11- Slides will be dehydrated through 95% ethanol for 2 minutes, 100% ethanol for 2×3 minutes
- 12- Finally, they will be cleared in xylene for 2-3 minutes and cover slipped with permanent mounting medium.

Since BMI-1 level is measured objectively then no blinding is required.

First: Calculation of Relative Quantification (RQ) (relative expression):

After the RT-PCR will run, the data will be expressed in Cycle threshold (Ct).PCR data sheets will include Ct values of assessed gene and the house keeping (reference) gene which will be continuously expressed in the cell- (β -actin).To measure the gene expression of certain gene, -ve control sample shall be used. So target gene expression will be assessed and related to reference (internal control) gene as follows:

Finally, RQ was calculated according to the following equation:

1. ΔCt (Cycle threshold) = Ct assessed gene – Ct reference gene
2. $\Delta\Delta Ct$ = ΔCt sample – Ct control gene
3. $RQ = 2^{-(\Delta\Delta Ct)}$

Second: Image analysis:

In order to provide more précis data on Bmi-1 immunoexpression in OSCC, image analyzer will be used.

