The data will be obtained using the software (SIS, Germany), which comprise a light microscope (Olympus B \times 60 Japan) capable of performing high speed digital image processing for the purpose of cell measurements. It will be calibrated automatically to convert the measurement units (pixels) produced by image analyzer program into actual micrometer units. In immunohistochemical sections, and by using the image analyzer, five specific fields showing maximum positivity of Bmi-1 expression will be used in each case; the mean of five values of each slide will be calculated and statistically will be analyzed. For each field of immunostained section, a measuring frame of area 1920000 pixels and then the area % will be calculated. The color of immunostaining will be automatically selected according to the positive control sections, converted into grey color then masked the red and white to allow automatic measurements by the computer system. Data obtained will be subjected to statistical analysis using Student-t test.

Since BMI-1 level is measured objectively then no blinding is required.

Sample size

The aim of the current study is to assess the validation of Bmi-1 detection at both protein and molecular levels in oral epithelial dysplasia and oral squamous cell carcinoma as a biomarker for early cancer detection versus biopsy embedded in paraffin blocks. We are going to apply a convenient consecutive sampling; it will include all archived blocks in the past 5 years (2012-2017) about 30 samples.

Statistical analysis methods:

Data will be analyzed using IBM SPSS advanced statistics (Statistical Package for Social Sciences), version 21 (SPSS Inc., Chicago, IL). Numerical data will be described as mean and standard deviation or median and range. Categorical data will be described as numbers and percentages. Correlation analysis will be used. Agreement between both methods will be analyzed with the use of kappa statistics.

References:

1. Nagadia, R., et al., *miRNAs in head and neck cancer revisited*. Cellular Oncology, 2013. **36**(1): p. 1-7.
2. Dalley, A.J., et al., *Expression of ABCG2 and Bmi-1 in oral potentially malignant lesions and oral squamous cell carcinoma*. Cancer medicine, 2014. **3**(2): p. 273-283.
3. Kurihara, K., et al., *Expression of BMI1 and ZEB1 in epithelial-mesenchymal transition of tongue squamous cell carcinoma*. Oncology reports, 2015. **34**(2): p. 771-778.

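### The printed ΔΔCt equation subtracts a single raw Ct instead of the control sample's ΔCt, so RQ is not relative to the control

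*Combined protocol and SAP*

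**What the plan says.** The PCR calculation is in section V (Methods) of the combined protocol and SAP, under the heading on relative quantification. It has three steps:

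1. ΔCt is "Ct assessed gene – Ct reference gene", with β-actin as the housekeeping gene.
2. ΔΔCt is "ΔCt sample – Ct control gene".
3. RQ is 2 raised to the power −ΔΔCt.

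The text just before the equations calls for a negative control (after the minus sign of its abbreviation it reads "ve control sample shall be used"). It continues: "So target gene expression will be assessed and related to reference (internal control) gene as follows". The word control is therefore used both for a sample and for β-actin. The term control gene is not defined, nor is the type of negative control sample, and no other section gives a different form of equation 2.

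Section IV asks "Which one of them is more sensitive and specific for Bmi-1 assessment, the protein or molecular levels". The statistical methods name correlation, without a type, and add: "Agreement between both methods will be analyzed with the use of kappa statistics". No RQ cut-off is stated. Step 13 of the PCR procedure also lists "amplification and quantitation of Bmi-1 receptor gene by real time PCR", so the calculation may apply to two genes.

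**The concern.** A relative quantity needs two differences. The first normalises each sample to its own β-actin. The second compares that value with the same normalised value in a control sample. Equation 2 keeps the first difference for the study sample but subtracts an un-normalised Ct for the control. A simple test shows the fault: the control, put through its own formula, must give RQ = 1.

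RQ is the end product of the PCR arm (ΔCt appears only as a step towards it), and PCR is one of the two methods being compared. Kappa, sensitivity and specificity all need RQ turned into categories. A wrong scale makes any fixed cut-off wrong. An error that differs between samples would also distort comparisons between blocks and the correlation with immunohistochemistry.

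**Working it through.** The plan states no RQ figure to reproduce, so the check is algebraic. Write T for target Ct and R for β-actin Ct, with s for a study sample and c for the control sample.

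**Correct form.** RQ = 2^−[(Ts − Rs) − (Tc − Rc)]. For the control this is 2^0 = 1.

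**Printed form.** RQ = 2^−[(Ts − Rs) − k], where k is one Ct. The term control gene allows three values of k: the control's target Ct (Tc), the control's β-actin Ct (Rc) or the sample's own β-actin Ct (Rs). The control returns 1 only if Tc − Rc = k. With β-actin subtracted, that means Tc = 2 × Rc. With the target subtracted, it means Rc = 0.

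**Illustration.** All Cts are assumptions, written target/β-actin: control 30/20 (ΔCt 10), sample A 28/20 (ΔCt 8), sample B 31/22 (ΔCt 9).

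| | Correct | k = control β-actin (20) | k = control target (30) | k = own β-actin |
|---|---|---|---|---|
| Control | 2^−(10−10) = 1 | 2^−(10−20) = 1,024 | 2^−(10−30) = 1,048,576 | 2^−(10−20) = 1,024 |
| A | 2^−(8−10) = 4 | 2^−(8−20) = 4,096 | 2^−(8−30) = 4,194,304 | 2^−(8−20) = 4,096 |
| B | 2^−(9−10) = 2 | 2^−(9−20) = 2,048 | 2^−(9−30) = 2,097,152 | 2^−(9−22) = 8,192 |
| A/B | 2 | 2 | 2 | 0.5 |

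**Fixed control value (columns 3 and 4).** Every RQ is multiplied by 2^(k − ΔCt of control): 2^10 = 1,024 or 2^20 = 1,048,576 here. For assumed control pairs from 24/16 to 30/24, the factor runs from 256 to 262,144 (β-actin subtracted) or from 65,536 to about 16.8 million (target subtracted). Ratios, ranks, correlations and t-tests on RQ are unchanged, provided one control value serves all samples. If the control differs by run, so does the factor.

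A fixed cut-off does not survive. RQ ≥ 2 means ΔCt ≤ c − 1, where c is the value subtracted. The correct c = 10 gives ΔCt ≤ 9; c = 20 gives ≤ 19 and c = 30 gives ≤ 29. With ΔCts near 8 to 10, all samples become PCR-positive. For 30 samples split 15/15 on immunohistochemistry, observed agreement is 15/30 = 0.5 and chance agreement is 1 × 0.5 + 0 × 0.5 = 0.5, so kappa = 0. For contrast, a 13/2/2/13 table gives (26/30 − 0.5)/(1 − 0.5) = 0.73. The cut-off of 2 is an assumption.

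**Own β-actin (column 5).** ΔΔCt becomes Ts − 2 × Rs. The control drops out and the amount of template no longer cancels. A β-actin difference of d cycles between two blocks distorts their RQ ratio by 2^d: 2-, 4- and 8-fold for d = 1, 2 and 3. The PCR procedure measures nucleic acid concentration but has no step that equalises input.

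A simulation of 15 against 15 samples shows the possible effect. It assumes a true log2 difference of 1, SD 1, a two-sided 5% t-test on the log2 scale, and β-actin Ct independent of expression. Power with the correct value is about 0.76.

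| SD of β-actin Ct between samples | Mean Spearman with correct value | Power |
|---|---|---|
| 0.5 | 0.89 | 0.66 |
| 1 | 0.71 | 0.47 |
| 2 | 0.46 | 0.20 |
| 3 | 0.33 | 0.14 |

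**The case against.** The strongest answer is that this is a misprint. The section is about relative quantification, names ΔΔCt and calls for a control sample, so the laboratory may well compute the right quantity. A Δ may also have been lost when the PDF was read. That cannot be excluded, but the other Δ symbols on the same line survive, and the noun would still have to be sample rather than gene. The text needs repair either way.

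Second, with a fixed control value the correlations and rank comparisons are unharmed. The kappa example rests on a cut-off that the plan does not state, and a median or ROC-derived cut-off would move with the scale and leave kappa unchanged. This stands. What remains is a wrong fold change against control and the failure of any fixed cut-off. The missing cut-off is a separate gap.

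Third, the own-β-actin reading is the more damaging but arguably the less natural. Equation 1 calls β-actin the reference gene, and this reading subtracts it twice and leaves the control sample with no role. That is a fair point. Yet the plan's own sentence introducing the equations labels β-actin an internal control gene, so an analyst following its vocabulary could arrive there.

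The Student t-test is mentioned in the image-analysis paragraph and is not clearly assigned to RQ, so its behaviour matters only if it is used there.

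**Conclusion.** The concern holds. Followed literally, equation 2 gives a wrong fold change against the control under every reading, apart from coincidental Ct values. If one fixed control Ct is subtracted, the error is a constant factor (1,024 or 1,048,576 in the illustration) and comparisons between samples stand. If each sample's own β-actin is subtracted, comparisons between blocks are distorted 2-fold per cycle of β-actin difference and can reverse.

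The fault in the formula needs no assumed figure. The sizes do: all Cts, SDs and the cut-off are assumptions, because the documents give none. Whether results would actually be wrong depends on what the laboratory computes, which the plan as written cannot settle. It should be corrected before any RQ is calculated.

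**What to change.** Replace equation 2 with ΔΔCt = ΔCt(sample) − ΔCt(control sample), where ΔCt(control sample) is the assessed gene's Ct minus the β-actin Ct, both measured in the control sample the plan already calls for. Apply it separately to each gene assessed, and confirm that the control returns RQ = 1.

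Add one sentence stating that the negative control is a tissue or pooled sample with a measurable Ct, not a no-template blank. If a blank was intended, either add one calibrator sample or analyse ΔCt directly, which needs no calibrator.

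The cost is one equation and one sentence. Only if the control is a blank is there more: one calibrator run alongside the study samples, or no added sample if ΔCt is analysed directly.

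### Blinding is waived because Bmi-1 is measured objectively, but the plan does not say whether software or a person picks the five most positive immunohistochemistry fields

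*Combined protocol and SAP*

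**What the plan says.** All references are to the combined protocol and SAP.

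- **Waiver.** Section V (Methods) states "Since BMI-1 level is measured objectively then no blinding is required". The sentence appears twice: after the last step of the immunohistochemistry procedures, and again directly after the image-analysis paragraph.
- **Field choice.** Under "Second: Image analysis" in Section V, "by using the image analyzer, five specific fields showing maximum positivity of Bmi-1 expression will be used in each case". The five area percentages are averaged to give one value per slide.
- **Automatic steps.** The same paragraph says of the system, "It will be calibrated automatically to convert the measurement units (pixels) produced by image analyzer program into actual micrometer units", and of the stain, "The color of immunostaining will be automatically selected according to the positive control sections". It also describes the measurement itself as automatic.
- **Use of the value.** "Data obtained will be subjected to statistical analysis using Student-t test". The groups are not named. The statistical analysis section adds correlation, and kappa for agreement between the two methods.
- **Nearest thing to a safeguard.** Under Participants, Bmi-1 data "will be collected prospectively from both the reference and index tests independently".

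**The concern.** The IHC value has two parts: choosing the fields, then measuring stained area inside them. Objective measurement of a field does not make the choice of that field objective. A score built from the strongest fields depends on how thoroughly the slide was searched: a less complete search misses strong fields and gives a lower score. If the person searching knows the diagnosis or grade, the search may be more thorough in one group than in another. If that person knows the PCR result, the search may be influenced by it, which would affect the apparent agreement between the two methods.

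Both comparisons matter to the study. The research question is "Does the expression of Bmi-1 vary from oral epithelial dysplasia to different grades of squamous cell carcinoma at protein and molecular levels", followed by which of the two levels is more sensitive and specific. The literature review reports higher Bmi-1 in more advanced lesions, so an unmasked selector would also know which result is expected.

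**Working it through.** **1. Which steps does the objectivity reason cover?**

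| Step towards the IHC value | What the image-analysis text says |
|---|---|
| Calibration | Automatic |
| Colour selection | Automatic, set from positive control sections |
| Choice of five fields | Done with the image analyzer; selector not stated |
| Area measurement in a field | Automatic, by the computer system |
| Mean of five values | Arithmetic |

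Field choice is the one step that involves judgement if a person performs it. It is also the one for which the text states neither automation nor a selector. The plan gives no rule for how much of the section is searched.

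**2. Is masking provided elsewhere?** No section codes the slides or withholds the diagnosis, grade or PCR result from whoever runs the image analysis. The word *independently* under Participants describes collecting reference and index data separately. It does not say that the operator lacks access to the other results, and the two later sentences waive blinding outright.

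**3. Which comparison would be affected?** The research question compares dysplasia with grades of carcinoma. The image-analysis paragraph, however, opens with "data on Bmi-1 immunoexpression in OSCC, image analyzer will be used", and the t-test groups are unnamed. The comparison could be dysplasia against carcinoma or one grade against another.

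**4. Can the bias be sized?** There is no figure in the plan to reproduce. About 30 samples are planned, with no alpha, power, effect size or standard deviation (SD). The two illustrations below assume a two-sided 5% pooled t-test, no true difference, and splits of 15 v 15 or 10 v 20. None of these inputs is in the documents.

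*Illustration A: a fixed shift.* Suppose field choice moves one group's mean by b SD. The noncentrality is b × √(n₁n₂/(n₁+n₂)), with 28 degrees of freedom and a critical value of 2.048. The root is √(225/30) = 2.739 for 15 v 15 and √(200/30) = 2.582 for 10 v 20.

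| b | Noncentrality, 15 v 15 | False-positive rate | Noncentrality, 10 v 20 | False-positive rate |
|---|---|---|---|---|
| 0 | 0 | 5.0% | 0 | 5.0% |
| 0.25 | 0.685 | 10.1% | 0.645 | 9.6% |
| 0.5 | 1.369 | 26.2% | 1.291 | 23.9% |
| 1.0 | 2.739 | 75.3% | 2.582 | 70.3% |

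*Illustration B: unequal searching.* Each slide has 20 candidate fields. The selector takes the five ranked highest, and the ranking has correlation r with true positivity. The between-slide SD is 1 and the within-slide SD is s. The expected shift is s × (r₁ − r₂) × 1.21, where 1.21 is the mean of the top five of 20 standard normal values. For r of 1 v 0.8 and s = 1 this is 0.2 × 1.21 = 0.24. Simulated false-positive rates (100,000 runs per cell), shown as s = 0.5 / s = 1:

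| r, group 1 v group 2 | 15 v 15 | 10 v 20 |
|---|---|---|
| 1 v 1 | 4.9% / 5.0% | 4.9% / 5.1% |
| 0.9 v 0.8 | 5.4% / 6.1% | 5.3% / 5.8% |
| 1 v 0.8 | 6.3% / 9.5% | 6.0% / 8.8% |
| 1 v 0.5 | 12.5% / 32.4% | 11.5% / 28.9% |

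Equal search accuracy leaves the error rate at 5%; unequal accuracy raises it. How far depends entirely on the chosen shift, r and s, so neither illustration sizes the problem in this study.

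**The case against.** **The software may select the fields.** The paragraph says the data are obtained using the software, and the fields are chosen by means of the image analyzer. This stands as a possibility. A reader might infer that a person certainly picks the fields and that the objectivity argument is therefore false. The documents do not support that. They leave the selector unstated, so the argument is unsupported for this step, not refuted. If software selects, the point falls away for field choice.

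**The criterion limits discretion.** The most positive fields are a defined extreme, not a free choice of representative ones. An operator who always finds the true top five gets the same value whatever they know. This stands: bias needs unequal searching, as the equal-accuracy row in illustration B shows. The plan, however, sets no search procedure to make searching equal.

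**Masking cannot hide the lesion.** Slides are counterstained with haematoxylin, so anyone viewing them may recognise dysplasia or carcinoma. This also stands, and it limits the benefit most for dysplasia against carcinoma. Codes still hide the recorded grade and the PCR result, and a common search procedure helps even where the lesion is recognised.

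**The effect may be small.** Modest accuracy differences in illustration B give 5% to 6%. A reader might infer that a realistic lapse would do little harm; from illustration A, a reader might infer serious harm. Neither inference is supported, because every input is assumed.

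**Conclusion.** The point holds as a cheap improvement. The plan makes an outright statement that no blinding is needed, and the reason given does not reach one step of the IHC measurement. That is more than missing detail, but it is not a demonstrated bias. It matters only if a person selects the fields with knowledge of the diagnosis, grade or PCR result. In that case the IHC group comparison and the agreement with PCR are exposed. Size and direction cannot be derived from the documents. The point does not extend to the PCR Ct readout, which involves no choice of fields.

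**What to change.** Withdraw the blinding waiver as far as it covers IHC, in both places, and state:

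- Slides carry random codes.
- Field selection and image analysis are done without access to the recorded diagnosis, the recorded grade or the PCR result.
- The same search procedure is applied to every slide, for example scanning the whole section before the five fields are chosen.

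The five-field measure stays as it is. If the software is meant to select the fields, one sentence saying so replaces these statements.

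The cost is two or three sentences, an estimated few hours to code about 30 slides, and some scanning time per slide. No extra reader or measurement is needed. The coding must be in place before fields are chosen. Because morphology stays visible, masking is partial, and the gain is surest for the PCR result and the recorded grade.

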Strong evidence suggested that Bmi1 was important to invasive potential and favored to the maintenance and self-renewal of CSCs in several tumor types, including HNSCC [44] [41] [24] [45]. As a stem cell marker, Bmi1 played a key role in the functioning of endogenous stem cells and CSCs [46] [45]. Additionally, it has been found to be related to many other CSC markers such as SOX2 [47], Oct4 [48], Nanog [48], ALDH1[32], ABCG2 [2] and CD44 [49] [50]. **Seo et al., 2011** found a connection between BMI-1 and Sox2 in maintaining self-renewal and identified BMI-1 as a key mediator of Sox2 function [47].

Moreover, recent studies have revealed that Bmi-1 expression was associated not only with the development of oral cancer, but also in patients with oral leukoplakia (LP)[40], oral erythroplakia[32], and oral lichen planus[42]. Furthermore, Bmi-1 overexpression was found in LP, and increased significantly from mild to moderate and severe LP. Consistent results were reported in Kang's research, which showed that Bmi-1 overexpression was observed in preneoplastic oral mucosal tissues, including mild, moderate or severe OED [51]. **Ma L et al., 2013** suggested that Bmi1 may act as a beneficial marker for the recognition of high risk of malignant progression of OLP [42].

Wang et al., 2015 studies have indicated that silencing BMI-1 can decrease the malignant biological behavior of cancer, in addition to the self-renewal and differentiation of CSCs. Therefore, BMI-1 was hypothesized to affect the malignant biological behavior of human tumors by regulating the self-renewal and differentiation of CSCs. In conclusion, BMI-1 might represent a hopeful target for the prevention and therapy of various types of human cancer. Further understanding the molecular mechanism underlying the regulation of BMI-1 in human cancer and CSCs is of extremely huge clinical value [52].

PIRT

P→ Diagnostic validity of Bmi-1 levels in archival paraffin embedded tissue samples of oral dysplasia and squamous cell carcinoma.

I 1 → Expression of Bmi-1 protein level by immunohistochemistry in oral dysplasia and squamous cell carcinoma.

I 2 → Expression of Bmi-1 molecule at RNA level by PCR in oral dysplasia and squamous cell carcinoma.

R→ biopsy embedded in paraffin blocks.

T→oral dysplasia and squamous cell carcinoma.

IV. Research Question:

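### The only group test named is a two-group Student t-test on the image-analysis data, but the research question spans dysplasia and several carcinoma grades at protein and RNA level

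*Combined protocol and SAP*

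**What the plan says.** Section IV (Research Question) asks: "Does the expression of Bmi-1 vary from oral epithelial dysplasia to different grades of squamous cell carcinoma at protein and molecular levels". Section V, Participants, describes data collection in the same terms: "Data regarding Bmi-1 antibody expression in oral dysplasia and different grades of squamous cell carcinoma will be collected prospectively". The total is "30 samples of oral dysplasia and squamous cell carcinoma", with no split between dysplasia and carcinoma or between grades, and no grading system.

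The one test that compares groups ends the paragraph headed Second: Image analysis: "Data obtained will be subjected to statistical analysis using Student-t test". The groups are not named. The sentence that introduces image analysis mentions carcinoma only ("data on Bmi-1 immunoexpression in OSCC, image analyzer will be used"). The aim, under Sample size, names two categories without grades ("in oral epithelial dysplasia and oral squamous cell carcinoma as a biomarker for early cancer detection").

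The section on relative quantification of the PCR data stops at the RQ formula and names no test. Statistical analysis methods lists descriptive summaries, kappa for agreement between the two methods, and "Correlation analysis will be used" without saying what is correlated with what. No significance level, multi-group test or adjustment rule appears anywhere.

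**The concern.** A t-test compares two groups. The question needs dysplasia and at least two carcinoma grades, for two markers. Someone who follows the Student-t sentence must either run it on several pairs or merge the grades into one carcinoma group. Several unadjusted pairs raise the chance of a spurious difference above 5%. Merging keeps that chance at 5% but leaves the comparison between grades unanswered. The PCR data have no group test at all.

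Since the plan does not choose, the choice could be made after the expression values are known. A reader of the results could not then tell a planned comparison from a selected one.

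**Working it through.** **No figure to reproduce.** The 30 samples come from what the archive holds. The plan gives no alpha, power, effect size, SD or group split.

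**Inputs.** From the plan: N = 30, dysplasia plus plural grades, two markers. Assumed, because the plan is silent: two-sided alpha 0.05, normal data with equal SD, and three or four groups. Layouts, with dysplasia first, are 10/10/10 and 15/8/7 for three groups, and 8/8/7/7 and 15/5/5/5 for four. Rates below are simulated unless a formula is shown.

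**1. Number of pairs per marker.** g(g − 1)/2 gives 3 for three groups and 6 for four.

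**2. Error if all pairs are t-tested without adjustment.** If the tests were independent, 1 − 0.95^3 = 14.3% and 1 − 0.95^6 = 26.5%. Pairs share groups, so the true values are lower: about 12% with three groups and 20–21% with four, per marker.

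If both markers were tested this way and were independent, the figures would be 1 − (1 − 0.122)^2 = 22.9% and 1 − (1 − 0.205)^2 = 36.8%. This needs a further assumption, because the plan names no t-test for PCR.

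**3. Error and power if grades are pooled.** The error is 4.9–5.1%. Power to detect some difference depends on the pattern:

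| Assumed pattern | Groups | Pooled t | ANOVA | Linear trend |
|---|---|---|---|---|
| Rise in 0.5 SD steps | 3 | 45–48% | 46% | 58% |
| Rise in 0.5 SD steps | 4 | 58–72% | 66–69% | 84–86% |
| All grades raised by 1.1 SD | 4 | 73–83% | 53–64% | – |
| Dysplasia 0; grades −1, 0, +1 SD (chosen worst case) | 4 | 2% | 69–87% | – |

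So pooling often costs little power, and sometimes gains some. What it always loses is which grades differ.

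**4. Effect of Holm adjustment within a marker.** With no true differences, the chance of any false pair falls to about 4–4.5%. Power for dysplasia against the top grade, under 0.5 SD steps, falls as follows (simulation error up to about one point):

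- Four groups (1.5 SD apart): from about 76–78% to 47–50%.
- Three groups (1.0 SD apart): from 55–56% to 37–38%.

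Holm controls the pairwise error by itself, so no significant ANOVA is needed first. Adding that condition lowers the same powers to 45–49% and 35–36%.

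**5. Error over both markers.** At 5% per marker, independent markers give 1 − 0.95^2 = 9.75%. The bound under any dependence is 5% + 5% = 10%.

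**The case against.** The strongest reply is that a t-test suits the stated aim, which names dysplasia and carcinoma as two categories. On that reading the test is valid, its error is 5%, and it can have more power than ANOVA. This stands as far as it goes. But the plan never says that this is the contrast, and the research question and the data-collection sentence both name grades.

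A second reply is that the correlation analysis may relate expression to ordered grade, which would be a trend analysis. That is possible. It could equally mean protein against RNA. With no variables named, it does not settle the matter.

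Third, the 12% and 20–21% rest on an all-pairs analysis that the plan does not describe, and on an assumed alpha, number of grades and split. This is right. A reader might infer that the study will run unadjusted pairwise tests and so carries a false-positive rate of 20% or more. The documents do not support that; the figures show only what one permitted reading would cost. Nor do they support the inference that the t-test is simply the wrong test, or that pooling must waste power.

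Finally, ANOVA against an ordered-trend test is a judgement. The literature review reports that "Bmi-1 overexpression was found in LP, and increased significantly from mild to moderate and severe LP", which makes a rise with grade a reasonable hypothesis, and for that pattern the trend test does better.

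**Conclusion.** The point holds as a mismatch between question and test. The research question needs a comparison over at least three groups for each of two markers; the plan supplies one two-group test, for one marker, with its groups unnamed. This does not depend on any assumed figure.

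The size does. With alpha 0.05, N = 30 and normal data, unadjusted testing of all pairs would give about 12% (three groups) or 20–21% (four groups) false positives per marker. Pooling would give 5% and no answer on grades. The plan does not say which would be done. It should be changed, and the change is a cheap improvement.

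**What to change.** Replace the Student-t sentence with text such as:

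> Before any expression data are seen, the grading system, the groups (dysplasia and each carcinoma grade) and a rule for merging sparse grades will be fixed. For each marker (Bmi-1 area %; PCR expression as ΔCt) one multi-group test across these groups will be made at two-sided 0.05: one-way ANOVA or Kruskal-Wallis, or an ordered-trend test if a rise with grade is the hypothesis. The choice will be made in advance. Pairwise comparisons will be Holm-adjusted within each marker. Dysplasia versus pooled carcinoma will be reported as a secondary difference with 95% CI.

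(ANOVA and Kruskal-Wallis have no direction, so two-sided applies to the trend and pairwise tests.)

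The groups must be fixed before expression data are seen, not merely before testing; otherwise grades could still be split or merged in the light of the results. ΔCt is proposed because RQ is an exponential transform, 2^−(ΔΔCt), and so likely skewed. With one common control value, log2 RQ differs from −ΔCt only by a constant, so group comparisons on the two are the same.

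Under Statistical analysis methods, also name the variables and the type of correlation.

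The cost is a few sentences, with no new samples or assays. Power for single pairs falls as shown in step 4 of the working. Error is controlled per marker, not over both; adjusting over both is optional.
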